6 STUDY OBJECTIVES AND ENDPOINTS

61 Study Objectives

The primary objective of this study is:

• To measure the effect of MP1032 plus SoC versus placebo plus SoC on Day 14 on disease progression in patients with moderate to severe COVID-19

The secondary objectives of this study are:

- To measure the effect of MP1032 plus SoC versus placebo plus SoC on Day 28 on disease progression in patients with moderate to severe COVID-19
- To measure the effect of MP1032 plus SoC versus placebo plus SoC on disease resolution on Day 14 and Day 28
- To measure the effect of MP1032 plus SoC versus placebo plus SoC on the mortality rate and other specific COVID-19 related characteristics
- To assess the safety of MP1032 (eg, AEs and laboratory abnormalities)
- To assess the PK of MP1032 on Day 1 (single dose) and Day 7 (steady state) in a PK subset of patients

The exploratory objectives of this study are:

- To measure the effect of MP1032 plus SoC versus placebo plus SoC on some additional COVID-19 related characteristics
- To evaluate the health-related quality of life (HRQoL) of patients treated MP1032 plus SoC compared with placebo plus SoC
- To evaluate biomarker levels

6.2 Study Endpoints

The primary efficacy endpoint of this study is:

• Proportion of patients with disease progression on Day 14. Disease progression is defined as the proportion of patients who are not alive or who have respiratory failure. Respiratory failure is defined as patients who have a score of 2, 3, or 4 on the National Institute of Allergy and Infectious Diseases (NIAID) 8-point ordinal scale (see below).

The key secondary efficacy endpoints of this study are:

- Proportion of patients with disease progression on Day 28. Disease progression is defined as the proportion of patients who are not alive or who have respiratory failure. Respiratory failure is defined as patients who have a score of 2, 3, or 4 on the NIAID 8-point ordinal scale (see below).
- Proportion of patients with disease resolution on Day 28. Disease resolution is defined as patients who are alive and have a score of 6, 7, or 8 on the NIAID 8-point ordinal scale.

This document is confidential.

Page 31 of 85

MP1032

MP1032-CT05	
Protocol v2.0	

- All-cause mortality rate at Day 28
- Change of clinical status related to COVID-19 on Day 28 compared with baseline according to the following NIAID 8-point ordinal scale:
 - 1. Death
 - 2. Hospitalized, on invasive ventilation (mechanical ventilator and/or extracorporeal membrane oxygenation [ECMO])
 - 3. Hospitalized, on non-invasive ventilation or high-flow oxygen devices
 - 4. Hospitalized, requiring supplemental oxygen
 - 5. Hospitalized, not requiring supplemental oxygen, but requiring ongoing medical care (COVID-19 related or otherwise)
 - 6. Hospitalized, not requiring supplemental oxygen and no longer requires ongoing medical care (used if hospitalization was extended for infection-control reasons)
 - 7. Not hospitalized, limitation on activities, and/or requiring home oxygen
 - 8. Not hospitalized, no limitations on activities

Please note: Patients requiring oxygen before COVID-19 and returning to baseline oxygen use will be considered improved (ie, not requiring supplemental oxygen). Patients with a limitation on activities before COVID-19 and returning to baseline activity will be considered improved. In case of death before Day 14 or Day 28, the patient will be considered with the NIAID score for death (score of 1) on the date of death in the analysis.

The other secondary endpoints of this study are:

- Proportion of patients with disease resolution on Day 14. Disease resolution is defined as patients who are alive and have a score of 6, 7, or 8 on the NIAID 8-point ordinal scale.
- All-cause mortality rate at Day 14 and Day 60
- Change of clinical status related to COVID-19 on Day 14 compared with baseline according to the NIAID 8-point ordinal scale as listed above
- Proportion of patients requiring invasive ventilation (mechanical ventilator and/or ECMO), or who are not alive on Day 14 or Day 28
- Proportion of patients in each category of the NIAID 8-point ordinal scale
- Time to (first) improvement of at least 1 category on the NIAID 8-point ordinal scale (until Day 28). Patients who did not improve at least 1 category on the NIAID scale or die before Day 28 will be censored at Day 28.
- The odds ratio between MP1032 and SoC and placebo and SoC for the number of patients with clinical status improvement from baseline on the NIAID 8-point ordinal scale (ie, an improvement of at least 1 category) at Day 14 and Day 28
- Total duration of hospitalization on Day 28 and Day 60 (from baseline to discharge; with death censored on the last day of the observed period at Day 28 or Day 60, respectively)

This document is confidential.

Page 32 of 85

MetrioPharm AG	MP1032-CT05	
MP1032	Final	
MetrioPharm AG	MP1032-CT05	
MP1032	Protocol v2.0	

- Proportion of patients alive and testing negative for COVID-19 on Day 14, Day 28, and Day 60
- Safety and tolerability assessed by:
 - Cumulative incidence of TEAEs (summarized by seriousness, severity, relationship to the study medication, outcome, and duration)
 - Vital sign parameters
 - Clinical laboratory parameters
 - Physical examination findings
- MP1032 plasma concentrations and PK parameters (if possible) including maximum observed plasma concentration, area under the concentration-time curve, elimination parameters, apparent body clearance, apparent volume of distribution, trough concentration, average observed plasma concentration at steady state, and other relevant PK parameters assessed via MP1032 plasma exposure on Day 1 and Day 7 in a PK subset of patients

Exploratory endpoints of this study are:

- Change in saturation of oxygen (SpO₂)/fraction of inspired oxygen (FiO₂) ratio (for patients alive) on Day 14 or Day 28 compared with baseline
- Total number of days in the intensive care unit (ICU)
- Duration of invasive mechanical ventilation
- Duration of ECMO
- Time to recovery from COVID-19 symptoms (stuffy or runny nose, sore throat, red or irritated eyes, shortness of breath, cough, low energy or tiredness, muscle or body aches, headache, chills or shivering, feeling hot or feverish, nausea, and number of times of vomit, times of diarrhea, sense of smell, sense of taste in the last 24 hours) at Day 14, Day 28, and Day 60
- Change from discharge in the EuroQol (EQ) index value and EQ visual analog scale (VAS) based on the EuroQol-5D-5L (EQ-5D-5L) questionnaire (Appendix 2) at Day 60
- Change from baseline in biomarker levels potentially including, but not limited to, cytokines (eg, C-reactive protein, interleukin [IL]-1β, IL-6, TNF-α, and IFN-γ), and other coagulation/inflammatory biomarkers (eg, D-dimer and ferritin)

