8.4 Study Withdrawal, Removal, and Replacement of Patients

Patients who terminate the study before Day 28 will be asked to complete the day-of-discharge study procedures. Patients who terminate the study after Day 28 will be asked to complete the Day 60 study procedures. Please note: It is expected that patients who discontinue the study drug early remain in the study, whenever possible, until the completion of the Day 60 study procedures. If it is not possible to follow-up with the patient until Day 60, then follow-up should occur until at least Day 28.

Once a patient is withdrawn from the study, the patient may not return to the study.

A patient may voluntarily withdraw or be withdrawn from the study at any time for the following reasons:

- patient withdrawal of consent (at any time, a patient's participation in the study may be terminated at his/her request)
- lost to follow-up: the patient stopped coming for visits, and study personnel were unable • to contact the patient.

Please note: In cases in which the patient is deemed lost to follow-up, the investigator or designee must make every effort to regain contact with the patient (eg, telephone calls, letter to the patient's last known mailing address, or local equivalent methods). In cases where the patient's LAR provides informed consent on behalf of the patient, the study site should attempt to contact the LAR. Additionally, the study site should attempt to regain contact with the patient using the alternative contact information provided by the patient/LAR at the time of informed consent. These contact attempts must be documented in the patient's medical records.

This document is confidential.

Page 41 of 85

MetrioPharm AG	MP1032-CT03			
MP1032	Final			
MetrioPharm AG	MP1032-CT05			
MP1032	Protocol v2.0			

The reason and date for patient withdrawal from the study must be recorded on the electronic case report form (eCRF).

Additionally, the sponsor or DMC may stop the study at any time for safety, regulatory, legal, or other reasons aligned with good clinical practice (GCP). This study may be terminated at the discretion of the sponsor or any regulatory agency. An investigator may elect to terminate or stop the study at his or her study site for any reason, including safety or low recruitment.

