15 STATISTICAL ANALYSIS

The statistical analysis plan (SAP) will provide further details regarding the definition of analysis variables and analysis methodology to address all study objectives. The SAP will be finalized before any statistical output (eg, DSMB output) is produced. The SAP will serve as a companion document to the protocol. The SAP will further describe the statistical analyses. All data will be included with the final CSR.

The statistical evaluation will be performed using $SAS^{(R)}$ software version 9.4 or higher (CCI \square).

Summary statistics will be presented by treatment group. Continuous and ordinal variables will be summarized by the number of patients (N), mean, standard deviation, median, minimum, and maximum for actual values and change from baseline. Additionally, for ordinal data, the number and percentage of patients in each category will be presented. Binary and categorical variables will be summarized for each treatment group by presenting the number and percentage of patients in the categories.

Statistical tests for comparison between treatments will be performed using a two-sided alpha level of 10%. No adjustment for multiple testing will be applied in this descriptive proof-of-concept study.

151 Determination of Sample Size

The primary efficacy endpoint "proportion of patients with disease progression on Day 14" is assumed to be 10% in the 300 mg MP1032 BID plus SoC treatment group (Arm A) and 30% in the placebo plus SoC treatment group (Arm B). Using the Chi-square test with type I error alpha=10% two-sided for this proof-of-concept study and 2:1 randomization ratio, with 114 randomized patients (76 in Arm A and 38 in Arm B) a statistical power of 83% can be achieved. Considering about 5% early study terminations, the necessary sample size to randomize results is 120 patients in total (80 in Arm A and 40 in Arm B). If during the conduct of the study the early study termination rate is higher than the estimated 5%, then an increase in the randomized number of patients may be necessary.

Sample size estimation was performed using nQuery 8, Version 8.6.1.0.

A subset of randomized patients will be consented for the collection of blood samples for PK measurements. The PK subset consists of approximately 20 patients from the 300 mg MP1032 BID plus SoC group and approximately 10 patients from the placebo plus SoC group, up to a total of approximately 30 patients.

This document is confidential.

Page 69 of 85

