15.3 Efficacy Analysis

The estimands for the primary efficacy endpoint, and for the 4 key secondary endpoints comparing the 2 treatment groups, will be tested with consideration of a two-sided type-1 error alpha of 10% for each test on the ITT. Additionally, 95% confidence intervals will be provided. Also, the treatment comparison with regards to the other secondary efficacy endpoints will be performed using a two-sided alpha level of 10%.

The main estimand for the primary efficacy endpoint is defined as follows:

This document is confidential.

Page 70 of 85

- Treatment: 300 mg MP1032 BID plus SoC in Arm A and placebo BID plus SoC in Arm B. If a patient terminates the study drug, but still remains in the study and is followed up, then the patient will continue to receive either SoC alone or SoC+ additional treatment. These treatments are defined with regards to intercurrent events as 'other treatments'.
- Population: Of all patients defined by the study inclusion/exclusion criteria, the analysis population will include patients who were randomized to study drug (ITT population).
- Variable: A binary variable indicating disease progression (death or respiratory failure) at Day 14. Respiratory failure is defined as patients who have a score of 2, 3, or 4 on the NIAID 8-point ordinal scale.
- Intercurrent events: All events that lead to study drug discontinuation and/or switch to other treatment before Day 14 will be handled using the treatment-policy strategy (ie, the NIAID score at Day 14 will be used for definition of the failure in such patients).
- Population-level summary: Common risk difference resulting from the Mantel-Haenszel (MH) test considering the 4 strata out of the combinations of the 2 randomization stratification factors disease severity (moderate versus severe) and ageclass (aged ≤65 years versus >65 years) at baseline.

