A similar analysis of covariance approach as described above for Day 28 will be applied for the analysis of the change of clinical status related to COVID-19 on Day 14 compared with baseline on the NIAID 8-point ordinal scale. The endpoint considering the proportion of patients requiring invasive ventilation (mechanical ventilator and/or ECMO) or who are not alive, the proportion of patients in each NIAID category, and the proportion of patients alive and testing negative for COVID-19 on Day 14, Day 28, and Day 60, respectively, will be compared between the treatment groups using MH test. Overall survival, time to (first) improvement of at least 1 category on the NIAID scale and total hospitalization duration (from baseline to discharge; with death censored on last day of the observed period – at Day 28 or Day 60, respectively – depending on the analyses) will be summarized using the Kaplan-Meier method and will be compared between treatment groups using log-rank tests. Additionally, Cox proportional hazards model will be applied with treatment and the 2 stratification factors as covariables.

This document is confidential.

Page 72 of 85

Final

MetrioPharm AG MP1032	MP1032-CT05	
	Final	
MetrioPharm AG	MP1032-CT05	
MP1032	Protocol v2 0	

The odds ratio between MP1032 and SoC and placebo and SoC for the number of patients with clinical status improvement from baseline on the NIAID 8-point ordinal scale (ie, an improvement of at least 1 category) at Day 14 and Day 28 will be analyzed using a logistic regression with consideration of the 2 stratification factors.

The time to recovery of all at baseline present COVID-19 symptoms (stuffy or runny nose, sore throat, red or irritated eyes, shortness of breath, cough, low energy or tiredness, muscle or body aches, headache, chills or shivering, feeling hot or feverish, nausea, and number of times of vomit, times of diarrhea, sense of smell, sense of taste in the last 24 hours) will be presented by Kaplan-Meier estimates and figure. The change from baseline will be presented in shift tables for each single symptom, with the number and percentage of subjects in each category at post-baseline assessment time-point compared to baseline for each treatment group.

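### Time to first improvement: living patients who leave the study unimproved before Day 28 are kept in the risk set, unobserved, until Day 28

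*Protocol*

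**What the plan says.** Protocol 6.2 lists time to first improvement of at least one NIAID category, up to Day 28, among the other secondary endpoints, with the rule "Patients who did not improve at least 1 category on the NIAID scale or die before Day 28 will be censored at Day 28". The synopsis repeats the sentence, as do the synopsis and 6.2 of the Bulgarian version.

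Section 15.3 states that this endpoint, with overall survival and hospitalization duration, "will be summarized using the Kaplan-Meier method and will be compared between treatment groups using log-rank tests", and adds a Cox model. Its only further censoring instruction there concerns death in the hospitalization-duration analysis. Multiple imputation and baseline carried forward are stated for the primary and key secondary endpoints, not for this one.

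Early departure is foreseen. Section 8.4 gives withdrawal of consent and loss to follow-up as reasons for leaving and adds "Once a patient is withdrawn from the study, the patient may not return to the study". Section 15.1 budgets for it: "Considering about 5% early study terminations, the necessary sample size to randomize results is 120 patients in total".

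**The concern.** A censoring time should be the last time at which the patient was known to be event-free. For a patient who completes Day 28 unimproved, that is Day 28. For a patient who dies unimproved, Day 28 is a deliberate and sound convention: death is treated as never improving. A living patient who leaves the study unimproved on Day 4 is a different case. Nothing is known after Day 4, yet the rule adds 24 event-free days (28 − 4).

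In effect, leaving is imputed as no improvement, without being declared as such. That differs from the rest of the plan. For the primary and key secondary NIAID endpoints the main analysis imputes from similar patients of the same arm, and missing counted as failure or non-resolution is only a sensitivity analysis for the binary endpoints (15.3). For hospitalization duration, only death is held at the end of the period (6.2).

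At stake are the level of the improvement curve and, if the arms lose different proportions, the comparison between them.

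**Working it through.** **The plan's own figure.** No figure is stated for this endpoint. The 83% power in 15.1 is for the Day 14 primary endpoint. It reproduces: pooled proportion (76 × 0.10 + 38 × 0.30)/114 = 0.1667; null SE = √(0.1667 × 0.8333 × (1/76 + 1/38)) = 0.0740; alternative SE = √(0.09/76 + 0.21/38) = 0.0819; (0.20 − 1.645 × 0.0740)/0.0819 = 0.955, which gives 83.0%. The inflation is 114/0.95 = 120, or 6 expected leavers. Only that last number bears on this point.

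**Inputs.** From the protocol: 80 and 40 patients, about 5% early terminations, two-sided alpha of 10% (15.1, 15.3). Assumed: exponential time to improvement with hazard 0.08 per day in both arms (no treatment effect), drop-out uniform over Days 1 to 7 and unrelated to prognosis, no deaths.

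**Level of the curve.** Under the written rule nobody is censored before Day 28, so the Kaplan-Meier estimate at Day 28 is simply the proportion with a recorded improvement:

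estimate = F(28) − d × [F(28) − mean F(D)],

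where F(t) = 1 − exp(−0.08 t), d is the fraction leaving and D the day of leaving.

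- F(28) = 1 − exp(−2.24) = 0.894.
- mean F(D) over Days 1 to 7 = 1 − (e^−0.08 − e^−0.56)/(0.08 × 6) = 0.267.
- The bracket is 0.894 − 0.267 = 0.627.

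| Drop-out d | Estimate, written rule |
|---|---|
| 2% | 0.894 − 0.02 × 0.627 = 0.881 |
| 5% | 0.894 − 0.05 × 0.627 = 0.862 |
| 10% | 0.894 − 0.10 × 0.627 = 0.831 |
| 12% | 0.894 − 0.12 × 0.627 = 0.818 |

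Simulation gives 86% to 86.5% at 5%. Censoring at the last assessment gives 89% to 90% throughout.

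**Size of the log-rank test at nominal 10%, by simulation.**

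| Drop-out, Arm A / placebo | Overall loss | Rejection, written rule |
|---|---|---|
| 5% / 5% | 5% | near 10% |
| 10% / 5% | (8 + 2)/120 = 8.3% | 10% to 12% |
| 7% / 2% | (5.6 + 0.8)/120 = 5.3% | about 12% |
| 12% / 2% | (9.6 + 0.8)/120 = 8.7% | about 18% (17% to 19% across runs) |
| 2% / 12% | (1.6 + 4.8)/120 = 5.3% | about 18% |

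Last-assessment censoring gives 8% to 11% in these settings. The gap at 12% against 2% is 0.881 − 0.818 = 0.063, about 6 points.

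**A second set of assumptions.** Take 80% true improvement by Day 28, all exits on Day 4, and exactly 6 leavers. Then F(4) = 1 − 0.2^(4/28) = 0.205.

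- Split 4:2, each arm reads 0.80 − 0.05 × 0.595 = 0.77.
- With all 6 in placebo (15% of that arm), placebo reads 0.80 − 0.15 × 0.595 = 0.71 against 0.80, and rejection is 22% (18% to 26% if true improvement is 70% to 90%).
- With all 6 in Arm A, rejection is 14%.
- Last-assessment censoring restores 0.80 in each arm and about 10% rejection.

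**The case against.** **The affected group is small.** This stands. Leaving must mean leaving the study. Discharge home scores 7 or 8, which is itself an improvement and so an event. Patients who only stop study drug are expected to remain under follow-up (8.4, 9.4). What remains is mainly unimproved inpatients who withdraw consent or are lost after a transfer. A reader might take the rule to mishandle discharged patients; it does not.

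**The test is barely affected at the planned loss.** This stands too. One might infer that any difference in drop-out turns into a spurious treatment effect. The figures do not support that: at 10% against 5%, or 7% against 2%, rejection stays at 10% to 12%. Rejection near 18% needs either more loss than planned (12% in Arm A, 8.7% overall) or, at 5.3% overall, three quarters of the leavers (4.8 of 6.4) in the smaller arm of a double-blind trial.

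**Counting leavers as unimproved is a recognised conservative convention.** Partly right. If leavers have a worse prognosis, last-assessment censoring overstates improvement. But the convention is not labelled here, and for the comparison it is not reliably conservative, because the bias can favour either arm.

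**The SAP can settle it.** Section 15 does leave the definition of analysis variables to the SAP, which is not shown. The protocol, however, does not leave this point open: it fixes a censoring time, and a SAP that used the last assessment would contradict it.

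**Improvement followed by death.** The clause on death could be read as cancelling an improvement that came first. The endpoint is time to first improvement, so that improvement is already the event. This is loose grammar, not an error in the plan.

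**Conclusion.** The point holds in limited form. The censoring rule is wrong for living patients who leave the study unimproved before Day 28, and right for deaths without improvement and for patients followed to Day 28. At a balanced 5% loss the Day 28 improvement estimate is about 3 points too low in each arm and the test keeps its size. A spurious difference of about 6 points, with about 18% rejection at nominal 10%, needs a marked imbalance such as 12% against 2%.

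These sizes rest on the assumed hazard, early exit and non-informative drop-out, none of which the protocol gives. The direction of the bias in the curve also depends on non-informative drop-out; that unobserved days are counted as event-free does not. This is one of several unadjusted secondary endpoints in a descriptive proof-of-concept study. It should be corrected, but it does not threaten the primary analysis.

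**What to change.** Replace the sentence with: *Patients who die without prior improvement, or complete Day 28 without improvement, are censored at Day 28. Living patients who leave the study before Day 28 without improvement are censored at their last NIAID assessment.*

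Make the change in 6.2, the synopsis, the same two places in the Bulgarian version, and any other country version with the sentence; align the SAP.

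No visits or data are added: Table 1 already schedules NIAID status on Days 1 to 14, on Day 28 and at early termination. The price is that last-assessment censoring assumes non-informative drop-out. Keeping the present rule as a labelled sensitivity analysis covers the case where leavers do worse.
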